1.2. Schema

1.3. Schedule of Activities (SoA)

Both treatment arms will use the same Screening Table ([Table 1](#)). Separate tables have been produced for the GSK3228836 treatment period ([Table 2](#) and [Table 3](#)). Both treatment arms will use the same PegIFN Treatment Table ([Table 4](#)), Reassessment of PegIFN Eligibility Tables ([Table 5](#) and [Table 6](#); only required if participant is ineligible to start PegIFN as per [Table 4](#)) and Off Treatment Follow-up Table ([Table 7](#)).

[China specific Schedule of Activities can be found in [Appendix 7: Country-specific requirements](#)]

Instructions that are applicable to all treatment arms include:

- In selected countries/sites, participants will have the option to use a centralised home nursing provider. Only selected visits will have the option to be performed as a home visit, these will include drug administration, blood draws, participant assessments and data collection. The full specifications of the home nursing services will be outlined in the Study Reference Manual (SRM).
- Haematology (platelet count) will be analysed at a local laboratory prior to each GSK3228836 dose. The blood draw can be taken the day before GSK3228836 dosing. Results must be available prior to dosing. Haematology samples will be collected for central laboratory assessments in parallel. After GSK3228836 treatment is completed, haematology is only collected centrally on weeks of clinic visits.
- If a participant is not eligible to start PegIFN, eligibility will be reassessed. If the participant does not become eligible after 13 weeks, PegIFN will not be initiated in order to ensure participants receive at least 12 weeks of PegIFN treatment. Irrespective of the week that a participant starts PegIFN, the final dose will be given on Study Week 48 for Arm 1 and Week 36 for Arm 2 ([Figure 1](#)).
- PegIFN dosing maybe self-administered at home, where local regulations allow at the visits indicated in the SoA ([Table 4](#)).

Figure 1 Schematic of Planned GSK3228836 and PegIFN Dosing Periods and Off Treatment Follow-up Period

[figure not shown]

Table 1 Screening (All Treatment Arms)

ASSESSMENTS	
Informed Consent (obtained any time prior to screening)	X
Inclusion and exclusion criteria	X
Demography	X
Medical history (includes substance usage) and current medical conditions	X
Medication history and concomitant medication review	X
Full physical exam including height and weight	X
Vital signs	X

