HBeAg (for participants HBeAg positive at screening)		X	X	X	X		X		X		X		X		X		X		X		X		X		X

PegIFN Dosing Week	1 ^a	2	3	4	5	6	7	8	9	10	11	12	13	14	15	16	17	18	19	20	21	22	23	24	
Window	±3 days																								
Complement C3, C4, C5a, Bb, hs-CRP, MCP-1			X		X				X					X			X				X				
ANCA, Ang II		X			X				X					X			X				X				
PK – PegIFN		X	X		X									X			X				X				
PK –GSK3228836		X		X							X			X											
HBV RNA, and sequencing (HBV genotype/phenotype; HBV DNA and/or RNA)		X	X		X			X		X				X			X				X				X
HBcrAg		X			X				X					X							X				
PBMC Collection for immunophenotyping ⁵		X			X									X											
Soluble Protein (immunology)		X	X		X									X			X				X				
PAXGene RNA for expression analysis in whole blood		X			X									X											
Archived Samples [serum; plasma]		X	X	X	X			X		X				X			X				X				X

- a. The first planned PegIFN visit occurs 7 days after the planned GSK3228836 dosing period.
- 1. Assessment of PegIFN eligibility should be based upon pre-dose safety assessments and laboratory assessments from previous visit
- 2. For specific Peg-IFN eligibility criteria please refer to protocol Section 4.1; **If ineligible for PegIFN refer to Table 5.**
- 3. If consistent with local regulations, participants are permitted to self-administer PegIFN at home, site staff may call to assess the participant by phone at this visit and no clinic visit is required. If local regulations or practices prefer to administer PegIFN within the clinic, this can be a clinic visit.
- 4. Participants in Japan are expected to return for a mid-week haematology assessment during Week 1 and at Week 5 and 7 in accordance with local regulations
- 5. Only for selected sites able to transport to the analysis lab as specified in the SRM

Table 5 Reassessment of PegIFN Eligibility

If a participant is ineligible for PegIFN dosing immediately (Week 1, [Table 4](#)), complete the SoA of PegIFN Eligibility Week 1, [Table 5](#).

Eligibility for PegIFN will be reassessed following the SoA in [Table 5](#) on PegIFN Eligibility Week 2, 3, 4, 6, 8, 10 and 13.

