4.1.2. Baseline Definition

For all endpoints (except as noted in baseline definitions) the baseline value will be the latest pre-dose assessment with a non-missing value, including those from unscheduled visits. If time is not collected, Day 1 assessments are assumed to be taken prior to first dose and used as baseline. If there are multiple assessments collected at the same scheduled time, the average of these assessments will be used as the baseline.

Unless otherwise stated, if baseline data is missing no derivation will be performed and baseline will be set to missing.

Baseline of estimated glomerular filtration rate (eGFR) is defined as the mean of all pre-dose values, from screening to Day 1 pre-dose assessment.

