Summary of post-baseline hepatobiliary laboratory abnormalities will be provided.

The worst-case urinalysis results post-baseline (on-treatment and off-treatment periods combined) relative to baseline will be summarized.

Summaries of result shifts from baseline, worst-case results post-baseline relative to baseline, and results with increase to \geq maximum toxicity grade post-baseline for chemistry, haematology, urinalysis, and immunology as applicable, will also be presented for treatment with GSK3228836 and PegIFN separately, by treatment arm and in total within each treatment period.

GSK3228836 liver chemistry monitoring and stopping event reporting will be summarized and listed. The liver monitoring and stopping criteria are described in the protocol Section 7.1.1.

GSK3228836 haematological monitoring and stopping events will be summarized and listed based on laboratory parameters (platelet count and anti-platelet antibodies). The haematological stopping criteria are described in the protocol Section 7.1.2.

GSK3228836 drug induced kidney injury (renal) monitoring and hold or stopping events will be identified programmatically and will be summarized and listed based on laboratory parameters (ACR, urinalysis red blood cells (RBC), serum creatinine, and eGFR). The kidney injury monitoring and stopping criteria are described in the protocol Section 7.1.3.

Drug induced vascular injury and complement monitoring/stopping event will be summarized and listed based on laboratory parameters (C3, C4, Bb, C5a, hs-CRP, MCP-1, p-ANCA, c-ANCA, eGFR, bilirubin, and platelet count). The drug induced vascular injury and complement monitoring and hold/stopping criteria are described in the protocol Section 7.1.4.

Hold/stopping event profile for GSK3228836 will be provided for any subject who has met hold or stopping criteria specified in protocol Section 7.1. Relevant information will be reported, including baseline characteristics, AEs/SAEs, concomitant medication, medical history/current medical conditions, study treatment administration details, laboratory values, and individual line plots of complement (C3/C4/C5a/Bb), inflammatory markers (hs-CRP/MCP-1), serum creatinine/creatinine clearance or eGFR/ACR, and platelet count.

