6.2.2. Study Phase and Period

Safety assessments and events will be classified according to the time of occurrence relative to the study intervention period.

Table 13 Study Phase Definitions

Study Intervention Phase	Definition
Pre-Treatment	For Assessments – Date ¹ ≤ Study Treatment Start Date For Events – Date ¹ < Study Treatment Start Date
On-Treatment	For Assessments – Study Treatment Start Date < Date ¹ < Last Treatment Stop Date + 7 days For Events – Study Treatment Start Date ≤ Date ¹ < Last Treatment Stop Date + 7 days
Post-Treatment	Date ¹ ≥ Last Treatment Stop Date + 7 days

¹ Date is the start date of the assessment/event.

Table 14 Study Period Definitions

Study Intervention Period	Definition
GSK3228836 Treatment Period	For Assessments – All Analysis Timepoints within : WK 1 DAY 1 to a day prior PEGIFN ELIGIBILITY WK 1 DAY 1* For Events – Study Treatment Start Date ≤ Date ¹ < GSK836 Last Treatment Date + 7 days
PegIFN Eligibility Period	For Assessments – All Analysis Timepoints within : 1) PEGIFN ELIGIBILITY WK 1 DAY 1 to a day prior PEGIFN DOSING WK 1 DAY 1* and 2) PEGIFN ASSESSMENT WK 14 to a day prior OT-W1 OT-DAY 1*

Study Intervention Period	Definition
	For Events – $GSK836 \text{ Last Treatment Date} + 7 \text{ days} \leq \text{Date}^1 < \text{PegIFN Treatment Start Date}$ *if subject withdrew or never received PegIFN dosing before PegIFN Dosing Visit then end of period would be 'Last PegIFN Assessment Week Stop Date + 7 days'
PegIFN Treatment Period	For Assessments – All Analysis Timepoints within : PEGIFN DOSING WK 1 DAY 1 to a day prior OT-W1 OT-DAY 1* For Events – $\text{PegIFN Treatment Start Date} \leq \text{Date}^1 < \text{PegIFN Treatment Stop Date} + 7 \text{ days}$
Follow-up Period	For Assessments – All Analysis Timepoints within : OT-W1 OT-DAY 1* onwards For Events – If subject never received PegIFN dosing and did not discontinue on-treatment - $\text{Date}1 \geq \text{Last PegIFN Assessment Week Stop Date} + 7 \text{ days}$ Else $\text{Date}1 \geq \text{Last Treatment Stop Date} + 7 \text{ days}$

¹ Date is the start date of the assessment/event.

* If a subject withdrew early or skipped period(s), consider start of next period analysis timepoint. If analysis timepoint is not collected, use corresponding planned start visit day in Section 6.2.8.

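### SAP Table 14 counts laboratory samples from the first PegIFN dosing day as PegIFN-period results, with no exception for pre-dose blood

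*SAP*

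**What the plan says.** SAP 6.2.2, Table 14 splits assessments into periods by analysis timepoint:

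- GSK3228836 Treatment Period: "WK 1 DAY 1 to a day prior PEGIFN ELIGIBILITY WK 1 DAY 1".
- PegIFN Eligibility Period (first part): "PEGIFN ELIGIBILITY WK 1 DAY 1 to a day prior PEGIFN DOSING WK 1 DAY 1".
- PegIFN Treatment Period: "PEGIFN DOSING WK 1 DAY 1 to a day prior OT-W1 OT-DAY 1".

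A footnote covers participants who pass straight from one drug to the other: "If a subject withdrew early or skipped period(s), consider start of next period analysis timepoint". For them, the GSK3228836 period ends the day before PegIFN Dosing Week 1 Day 1.

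Table 13, in the same section, defines the pre-treatment and on-treatment phases. It places an assessment dated on the study treatment start date in the pre-treatment phase, and an event dated that day in the on-treatment phase. SAP 4.1.2 has the same logic for baseline: "If time is not collected, Day 1 assessments are assumed to be taken prior to first dose and used as baseline".

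SAP 4.5.3.1 says that the shift, worst-case and grade-increase laboratory summaries "will also be presented for treatment with GSK3228836 and PegIFN separately, by treatment arm and in total within each treatment period". These summaries inherit the Table 14 boundaries.

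**The concern.** Blood drawn before the first PegIFN injection cannot show an effect of PegIFN. It can show an effect of GSK3228836, for which Protocol 4.3 gives a half-life of about 3 weeks. Table 14 nevertheless counts that sample as PegIFN.

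The Day 1 sample for GSK3228836 does no harm inside its own period, because it is the baseline. The PegIFN Day 1 sample has no such protection. SAP 4.1.2 sets no separate PegIFN baseline, so the sample counts as a post-baseline PegIFN value.

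What is at stake is attribution between the two drugs. Protocol 8.3.7 lists ALT increase, thrombocytopenia and renal injury as events of special interest for GSK3228836. Protocol 2.3.1 lists ALT flares and falling platelet counts as risks of PegIFN. The by-period tables are meant to separate these. The PegIFN start decision does not filter this sample either, because Protocol Table 4 says "Assessment of PegIFN eligibility should be based upon pre-dose safety assessments and laboratory assessments from previous visit".

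**Working it through.** **1. Planned days, reproduced from the plan.** SAP Table 19 puts GSK3228836 week x at day 1 + 7(x − 1). It puts PegIFN dosing week y at 1 + 7(23 + y + z) in Arm 1 and 1 + 7(11 + y + z) in Arm 2, where z is the number of ineligible weeks before PegIFN.

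| | Arm 1 | Arm 2 |
|---|---|---|
| Last GSK3228836 visit (x = 24 or 12) | 1 + 7×23 = 162 | 1 + 7×11 = 78 |
| PegIFN week 24, z = 0 | 1 + 7×47 = 330 | 1 + 7×35 = 246 |
| PegIFN week 1, z = 0 | 1 + 7×24 = 169 | 1 + 7×12 = 85 |

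The first two rows match the target days in SAP Tables 2 and 3. The third falls 7 days after the last GSK3228836 visit, as Protocol Table 4 footnote a says.

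**2. What the GSK3228836 period contains for immediate starters.** It ends on Day 168 (Arm 1) or Day 84 (Arm 2). No sample is scheduled on Days 163–168 or 79–84. The last one inside is on the day of the last planned dose, and for platelets it precedes that dose: the count "will be analysed at a local laboratory prior to each GSK3228836 dose". So the period holds no scheduled sample after the last planned dose in either arm.

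**3. What is drawn on Day 169/85.** Protocol Table 4 marks haematology, chemistry and urine ACR at PegIFN Week 1. As extracted, the complement, hs-CRP and MCP-1 row starts at Week 2, so those markers are not affected.

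**4. Delayed starters.** Eligibility week u falls on 1 + 7(23 + u) or 1 + 7(11 + u). Starting at Eligibility Week 2, 4 or 13 gives first PegIFN days 176, 190 and 253 in Arm 1 (92, 106 and 169 in Arm 2). There are 1, 3 and 7 earlier samples respectively, all in the Eligibility Period. Their first-PegIFN-day sample is also counted as PegIFN.

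**5. Share of samples.** Protocol Tables 2 and 3 schedule post-baseline haematology and chemistry weekly from Day 8: 23 draws to Day 162 and 11 to Day 78. With the Day 169/85 draw these become 24 and 12, so the reassigned sample is 1/24 = 4% and 1/12 = 8%. On the PegIFN side it is 1 of the 14 chemistry draws in Table 4 (7%).

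**6. Drug still present.** With a 3-week half-life, 2^(−7/21) = 0.79 of the amount remains 7 days after the last dose.

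**7. Illustration (hypothetical values).** Platelets are 105 × 10⁹/L on Day 162 and 80 × 10⁹/L on Day 169, before PegIFN. The first value is above the hold range in Protocol Table 10 and the limit in Protocol Table 8. As written, the by-period tables show a GSK3228836 worst value of 105 (if nothing earlier was lower) and a PegIFN value of 80.

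**8. The SAP's own efficacy windows.** SAP Tables 2 and 3 close the end-of-GSK3228836 window at the earlier of Day 182 (Arm 2: Day 98) and the first PegIFN dosing day. Adjacent windows there (for example 350, then 351) show that end days are included. For an immediate starter the window closes on Day 169 or 85, so HBsAg and HBV DNA from that visit count towards the end of GSK3228836. Table 14 puts the safety samples from the same visit under PegIFN.

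**The case against.** The best defence is that Table 14 follows a consistent rule. It starts both drugs' assessment periods on their Week 1 Day 1, and it ends GSK3228836 events at less than 7 days after the last dose. Since 162 + 7 = 169 and 78 + 7 = 85, laboratory values and events share a boundary. This explains where the line falls. It does not justify counting an apparently pre-dose sample as PegIFN, and Table 13 shows that the SAP is willing to treat same-day assessments and events differently.

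Several other points stand and limit the concern:

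- Pre-dose timing of the PegIFN Week 1 safety samples is inferred. Protocol 8.5 states it for PK samples, and Protocol 1.3 states it for platelets during GSK3228836 dosing.
- The overall shift and worst-case tables combine all post-baseline data and keep the value. Investigators also attribute each adverse event to GSK3228836, PegIFN or both (SAP 4.5.2).
- Only the last of 26 (Arm 1) or 14 (Arm 2) planned doses is concerned. Carry-over also continues into later PegIFN samples: 2^(−14/21) = 0.63 remains at PegIFN Week 2. Those later samples reflect both drugs, whereas a pre-dose Week 1 sample does not.
- Safety is an exploratory, descriptive objective.

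A reader might infer that the GSK3228836 tables can never show the effect of the last dose. The documents do not support that. Unscheduled samples between visits, early-termination samples windowed to the last GSK3228836 week (to Day 165 or 81), and on-schedule samples after early discontinuation of GSK3228836 can all fall in the period. Nor is the first-PegIFN-day sample the only scheduled one after GSK3228836 for everyone, since delayed starters have 1 to 7 before it.

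A reader might also want the GSK3228836 period extended to Eligibility Week 1, because SAP 4.5.3.1 specifies no by-period laboratory table for the Eligibility Period. Given the 7-day rule used throughout Tables 13 and 14, that is a preference rather than a correction.

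**Conclusion.** The point holds in a limited form. Table 14 assigns first-PegIFN-day laboratory samples to PegIFN without a pre-dose exception, unlike the treatment of first-day assessments for the first drug in Table 13 and SAP 4.1.2. For immediate starters who completed GSK3228836 as planned, this removes from the GSK3228836 by-period tables the only scheduled haematology, chemistry and ACR sample after the last planned dose, and adds it to the PegIFN tables.

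The effect is confined to by-drug attribution of ALT, platelet and renal changes. It is one scheduled sample per participant, a larger fraction in Arm 2 (8%) than in Arm 1 (4%). How many worst grades would change cannot be known from the plan. The conclusion assumes that the Week 1 safety blood is drawn before the injection. If sites draw it afterwards, the sample no longer strictly precedes PegIFN, although it would still be the first scheduled one after GSK3228836.

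**What to change.** In Table 14, change the assessment rules only:

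- Assign assessments dated on or before the first PegIFN dose date to the preceding period. That is the GSK3228836 Treatment Period for immediate starters and the PegIFN Eligibility Period for delayed starters.
- Start the PegIFN Treatment Period for assessments after that date.
- Align the footnote on skipped periods, and state the assumption that first-day safety samples are pre-dose.
- Leave the event rules as they are.

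The cost is a small derivation change and no new data. GSK3228836 worst-grade counts may rise slightly and PegIFN counts may fall. Laboratory values and adverse events dated on the first PegIFN day will sit in different periods, as first-day assessments and events already do in Table 13.

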6.2.3. Study Day and Reference Dates

The study reference date is the study treatment start date and will be used to calculate study day for safety and efficacy measures.

The study day is calculated as below:

- Assessment Date = Missing → Study Day = Missing
- Assessment Date < Reference Date → Study Day = Assessment Date – Reference Date
- Assessment Date ≥ Reference Date → Study Day = Assessment Date – Reference Date + 1

6.2.4. Multiple Measurements at One Analysis Time Point

Table 15 Multiple Measurements at One Analysis Time Point

Definition

 • Handling of multiple measurements within an analysis window for primary endpoint is described in Section 4.2.2 • Assessments on unscheduled visit will not be included in the tables of summary statistics by visit but will be included in the associated listings. Also, such assessments on unscheduled visit will be used for the "any time on-treatment" or "Any visit post-baseline" time point. • If there are multiple assessments on scheduled visit within visit window, will query the site to identify the valid assessment as the assessment for the scheduled visit. • Participants having both High and Low values for Normal Ranges at any post-baseline visit for safety parameters will be counted in both the High and Low categories of "Any visit post-baseline" row of related summary tables. • If after window assignment of Early Termination visits there are multiple valid assessments of a parameter within the same window (see Section 6.2.8), then the following hierarchy will be used to determine the value to be used for summary statistics of observed values: 
 ○ the assessment closest to the window target Study Day. ○ if there are multiple assessments equidistant from the target Study Day, then the mean of these values will be used. • If normal LAB ranges are collected and there are duplicate LAB records at the same date/timepoint, the the "worst-case" value will be selected. Specifically: 
 ○ For LAB result > Lower Normal range, select Maximum of Lab result (AVAL). ○ For LAB result <= Lower Normal range, select minimum of Lab result (AVAL).

6.2.5. Study Phases for Concomitant Medication

Please refer to Section 6.2.9 for handling of missing and partial dates for concomitant medication. Use the rules in this table if concomitant medication date is completely missing.

Table 16 Definition of Prior and Concomitant Medications

Study Phase	Definition
Prior	A prior medication is defined as any medication that has ended prior to the date of first dose of study drug.
Concomitant	Medications initiated after the first dose of study drug or initiated prior to the first dose of study drug and continued after the first dose of study drug will be counted as concomitant medications. A medication cannot be determined as prior or concomitant medication due to partially or completely missing start/stop date will be counted as both prior and concomitant medication.

6.2.6. Treatment Emergent Flag for Adverse Events

If the study treatment stop date is missing, then the AE will be classified as on-treatment.

Time of study treatment dosing and start/stop time of AEs should be considered, if collected.

Table 17 Definition of Treatment Emergent Adverse Events

Flag	Definition
Treatment Emergent	• Study Treatment Start Date \leq AE Start Date

6.2.7. METAVIR Fibrosis Score

The METAVIR score determined from the Fibrosis score is presented in table below.

Table 18 METAVIR Fibrosis Score

Fibrosis Score	METAVIR	Comment
≤ 0.21	Stage F0	No fibrosis
$>0.21 - 0.27$	F0-F1	
$>0.27 - 0.31$	F1	Portal Fibrosis
$>0.31 - 0.48$	Stage F1 – F2	
$>0.48 - 0.58$	Stage F2	Bridging fibrosis with few septa
$>0.58 - 0.72$	Stage F3	Bridging fibrosis with many septa
$>0.72 - 0.74$	Stage F3 – F4	
>0.74	Stage F4	Cirrhosis

<https://www.labcorp.com/tests/related-documents/L9465>, accessed 11Jan2022.

6.2.8. Assessment Windows for Early Termination

Unless otherwise specified, no windowing will be applied to unscheduled visits. Planned time relative to dosing will be used in figures, summaries, statistical analyses, and calculation of any derived parameters, unless otherwise stated. Unscheduled visits will not be included in summary tables and/or figures except from determining response for primary endpoint as described in Section 4.2.2 and summaries over “any time on treatment” or “any visit post-baseline”. Unscheduled visits will be included in listings.

Laboratory and vital signs data collected at Early Termination Visits will be assigned to assessment windows, according to the actual date.

Table 19 Early Termination Visit Windowing

Analysis Set / Domain	Target study day	Analysis Window		Analysis Timepoint
		Start day	End day	
GSK3228836 Arm 1 and Arm 2				
Lab, Vital Signs	1	1	2	Week 1 Day 1
	4	3	6	Week 1 Day 4
	8	7	9	Week 2 Day 8
	11	10	12	Week 2 Day 11
	15	13	18	Week 3 Day 15
	22	19	25	Week 4 Day 22
	$1+7*(x-1)$	$1+7*(x-1)-3$	$1+7*(x-1)+3$	Week x Day $1+7*(x-1)$
PegIFN Arm 1 Dosing Weeks*				
Lab Vital Signs	$1+7*(23+y+z)$	$1+7*(23+y+z)-3$	$1+7*(23+y+z)+3$	PegIFN Dosing Week y Day 1
PegIFN Arm 2 Dosing Weeks*				
Lab Vital Signs	$1+7*(11+y+z)$	$1+7*(11+y+z)-3$	$1+7*(11+y+z)+3$	PegIFN Dosing Week y Day 1
PegIFN Arm 1 Eligibility (No Dosing) Weeks (up to 13)				
Lab Vital Signs	$1+7*(23+u)$	$1+7*(23+u)-3$	$1+7*(23+u)+3$	PegIFN Eligibility Week u Day 1
PegIFN Arm 2 Eligibility (No Dosing) Weeks (up to 13)				
Lab Vital Signs	$1+7*(11+u)$	$1+7*(11+u)-3$	$1+7*(11+u)+3$	PegIFN Eligibility Week u Day 1

Analysis Set / Domain	Target study day	Analysis Window		Analysis Timepoint
		Start day	End day	
PegIFN Arm 1 No Dosing Assessment Weeks (week 14 onwards)				
Lab Vital Signs	$1+7*(23+v)$	$1+7*(23+v)-3$	$1+7*(23+v)+3$	PegIFN Assessment Week v
PegIFN Arm 2 No Dosing Assessment Weeks (week 14 onwards)				
Lab Vital Signs	$1+7*(11+v)$	$1+7*(11+v)-3$	$1+7*(11+v)+3$	PegIFN Assessment Week v
Off-Treatment Week (OTW) Follow-up Arm 1				
Lab Vital Signs	337	334	340	Off-Treatment Week 1
	344	341	347	Off-Treatment Week 2
	358	348	372	Off-Treatment Week 4
	386	373	400	Off-Treatment Week 8
	414	401	435	Off-Treatment Week 12
	456	436	477	Off-Treatment Week 18
	498	478	518	Off-Treatment Week 24
Off-Treatment Week (OTW) Follow-up Arm 2				
Lab Vital Signs	253	250	256	Off-Treatment Week 1
	260	257	263	Off-Treatment Week 2
	274	264	288	Off-Treatment Week 4
	302	289	316	Off-Treatment Week 8
	330	317	351	Off-Treatment Week 12
	372	352	393	Off-Treatment Week 18

Analysis Set / Domain	Target study day	Analysis Window		Analysis Timepoint
		Start day	End day	
	414	394	435	Off-Treatment Week 24
	456	436	477	Off-Treatment Week 30
	498	478	518	Off-Treatment Week 36

* Only if subject started PegIFN treatment.

1. Week x includes on-treatment weeks 5 – 24 for treatment with GSK3228836.
2. Week y includes on-treatment weeks 1 – 24 for treatment with PegIFN.
3. Week u includes PegIFN Eligibility weeks 1 – 13.
4. Week v includes PegIFN Eligibility weeks 14 – 24.
5. z is the total number of PegIFN ineligibility weeks prior to PegIFN treatment.
6. Visit windows are to be used for windowing of Early Termination visits only.

